9.2.3 Pregnancy Test

A urine pregnancy test will be obtained from female subjects who are of childbearing age at the Baseline Visit prior to administration of the study drug. For anuric (dialysis) participants, blood pregnancy tests will be obtained to rule out pregnancy during the week preceding the administration of the study drug.

9.3 Pharmacokinetic Measurements

Blood for determination of serum concentrations of deuterated 25(OH)D₃ and its metabolites will be collected at Study Visits 2-10.

At Baseline, blood will be drawn prior to administration of study drug as well as 5 minutes and 4 hours after administration.

9.4 Research Laboratory Measurements

Novel products of 25(OH)D₃ catabolism, including 4β,25(OH)₂D₃ and 25(OH)D₃-3-sulfate will be measured using LC-MS/MS, as previously described.⁵⁷ 25(OH)D₃-3-sulfate will be extracted from plasma.

10 EVALUATIONS BY VISIT

10.1 Screening Visit (Study Visit 0)

The following activities will occur during the screening visit:

- Collect signed consent form
- Confirm successful completion of CLEAR or CLEAR-CF protocol
- Perform focused medical history restricted to study eligibility criteria
- Complete medication inventory through EMR and patient report
- Participants who meet eligibility criteria at the screening visit will be prescribed vitamin D₃, 2000 IU daily by mouth

10.2 Re-screening Visit (Study Visit 1)

The Re-screening Visit will take place approximately 90 days after the Screening Visit (allowable range 60-180 days). The following activities will occur during the re-screening visit:

- Confirm adherence ($\geq 80\%$) to study vitamin D₃ (by self-report and pill count)
- Repeat focused medical history restricted to study eligibility criteria
- Complete medication inventory through EMR and patient report.
- Physical Exam (height and weight), and Vital Signs (blood pressure, heart rate)
- Collect non-fasting blood sample for measurement of complete blood count and total 25(OH)D.
- Collect non-fasting blood sample for serum sodium, potassium, chloride, bicarbonate, random glucose, BUN, creatinine, AST/SGOT, ALT/SGPT, albumin, calcium, and phosphorous.
- Participants who continue to meet eligibility criteria, at the screening visit and who are adherent ($\geq 80\%$) to study vitamin D₃, will be invited to return for the remaining study visits.
- Provide selected subjects with supplies required for first 24-hour urine collection

10.3 Baseline Visit (Study Visit 2, Day 0)

Visit 2 will take place at the University of Washington Clinical Research Center (CRC) or a suitable alternate facility and will last approximately 5 hours. Visit 2 will take place at least 90 days after Visit 0 and no more than 90 days after Visit 1. If more than 90 days elapse between Visits 1 and 2, screening procedures may be repeated to verify continued eligibility. The following activities will occur during the baseline visit:

- Perform a complete medical history
- Review current medications.
- Physical Exam (height and weight), and Vital Signs (blood pressure, heart rate)
- Complete physical activity and food frequency questionnaires.
- Pregnancy test for women of childbearing potential
- Collect blood **prior to administration of study drug** for measurement of basic chemistries, vitamin D metabolites, parathyroid hormone (PTH), and other measurements related to kidney disease and vitamin D metabolism.
- Collect urine sample from first 24-hour collection period. Sample will be used for measurement of albumin, creatinine, vitamin D binding protein, and vitamin D metabolites:
- Administer D₆-25(OH) D₃ intravenously.

- Collect blood 5 minutes and 4 hours post-infusion for measurement of vitamin D metabolites.
- Distribute supplies for second 24-hour urine collection.

10.4 Study Visit 3 (Day 1)

This visit is expected to last less than one hour. The following activities will occur during Visit 3:

- Collect urine sample from second 24-hour collection period.
- Collect blood for measurement of serum vitamin D metabolite concentrations.

10.5 Study Visit 4 (Day 4)

This visit is expected to last less than one hour. A window of one day before or after the scheduled date will be allowed when needed. Blood will be collected for measurement of serum vitamin D metabolite concentrations.

10.6 Study Visit 5 (Day 7)

This visit is expected to last less than one hour. A window of one day before or after the scheduled date will be allowed when needed. The following activities will occur during Visit 7:

- Collect blood for measurement of serum vitamin D metabolite concentrations.
- Collect blood for serum sodium, potassium, chloride, bicarbonate, random glucose, BUN, creatinine, aspartate aminotransferase (AST/SGOT), alanine aminotransferase (ALT/SGPT), albumin, calcium, and phosphorous at Study Visit 5 (Day 7) to monitor study safety.

10.7 Study Visits 6-10 (Day 14, 21, 28, 42, and 56)

Each of these visits is expected to last less than one hour. A window of up to 3 days before or after the scheduled date will be allowed when needed. Blood will be collected at each visit for measurement of serum vitamin D metabolite concentrations. Medication inventory will be repeated at Visit 10 (Day 56).

11 ADVERSE EXPERIENCE REPORTING AND DOCUMENTATION

11.1 Adverse Events

An adverse event (AE) is any symptom, sign, illness or experience that develops or worsens in severity during the course of the study. Intercurrent illnesses or injuries should be regarded as adverse events. Abnormal results of diagnostic procedures are considered to be adverse events if the abnormality:

- results in study withdrawal
- is associated with a serious adverse event
- is associated with clinical signs or symptoms
- leads to additional treatment or to further diagnostic tests
- is considered by the investigator to be of clinical significance

11.1.1 AE Severity

The National Cancer Institute's Common Terminology Criteria for Adverse Events (CTCAE) Version 3.0 should be used to assess and grade AE severity, including laboratory abnormalities judged to be clinically significant. The modified criteria can be found in the study manual. If the experience is not covered in the modified criteria, the guidelines shown in Table 11.1 below should be used to grade severity. It should be pointed out that the term "severe" is a measure of intensity and that a severe AE is not necessarily serious.

Table 11.1 AE Severity Grading

Severity (Toxicity Grade)	Description
Mild (1)	Transient or mild discomfort; no limitation in activity; no medical intervention or therapy required. The subject may be aware of the sign or symptom but tolerates it reasonably well.
Moderate (2)	Mild to moderate limitation in activity, no or minimal medical intervention/therapy required.
Severe (3)	Marked limitation in activity, medical intervention/therapy required, hospitalizations possible.
Life-threatening (4)	The subject is at risk of death due to the adverse experience as it occurred. This does not refer to an experience that hypothetically might have caused death if it were more severe.

11.1.2 AE Relationship to Study Drug

The relationship of an AE to the study drug should be assessed using the following the guidelines in Table 11.2.

Table 11.2 AE Relationship to Study Drug

Relationship to Drug	Comment
Definitely	Previously known toxicity of agent; or an event that follows a reasonable temporal sequence from administration of the drug; that follows a known or expected response pattern to the suspected drug; that is confirmed by stopping or reducing the dosage of the drug; and that is not explained by any other reasonable hypothesis.
Probably	An event that follows a reasonable temporal sequence from administration of the drug; that follows a known or expected response pattern to the suspected drug; that is confirmed by stopping or reducing the dosage of the drug; and that is unlikely to be explained by the known characteristics of the subject's clinical state or by other interventions.

Possibly	An event that follows a reasonable temporal sequence from administration of the drug; that follows a known or expected response pattern to that suspected drug; but that could readily have been produced by a number of other factors.
Unrelated	An event that can be determined with certainty to have no relationship to the study drug.

11.2 Serious Adverse Experiences (SAE)

An SAE is defined as any AE occurring at any dose that results in any of the following outcomes:

- death
- a life-threatening adverse experience
- inpatient hospitalization or prolongation of existing hospitalization
- a persistent or significant disability/incapacity
- a congenital anomaly/birth defect

Other important medical events may also be considered an SAE when, based on appropriate medical judgment, they jeopardize the subject or require intervention to prevent one of the outcomes listed.

A serious adverse event is any AE that is:

- fatal
- life-threatening
- requires or prolongs hospital stay
- results in persistent or significant disability or incapacity
- a congenital anomaly or birth defect
- an important medical event

Important medical events are those that do not fit the other definitions of serious adverse events, but the event may jeopardize the patient and may require treatment to prevent one of the listed serious adverse events.

Adverse events will be collected if they occur between the time of informed consent and up to 30 days after the last study visit. All unresolved adverse events will be followed by the PI until resolution, the adverse event is otherwise explained, or the participant is lost to follow-up. At the last study visit, the investigator will instruct each participant to report any subsequent event that the participant, or participant's personal physician, reasonably believes may be related to the study. The investigator will notify the study sponsor of any death or adverse event occurring after the participant has discontinued participation if the event can be reasonably related to the study.

11.3 Abnormal lab values

An abnormal clinical laboratory value will be documented as an adverse event if one of the following applies:

1. The abnormality is not contradicted by a repeat test to confirm the abnormality.

2. The abnormality suggests a disease and/or organ toxicity.
3. The abnormality is of a degree that requires active management (e.g., requires a medication change, more frequent follow-up, or further diagnostic evaluation).

11.4 Hospitalization, Prolonged Hospitalization or Surgery

Any adverse event that results in hospitalization or prolonged hospitalization will be documented and reported as a serious adverse event unless specifically instructed otherwise in this protocol. Any condition responsible for surgery will be documented as an adverse event if the condition meets the criteria for an adverse event. Neither the condition, hospitalization, prolonged hospitalization, nor surgery are reported as an adverse event in the following circumstances:

1. Hospitalization or prolonged hospitalization for diagnostic or elective surgical procedures for a preexisting condition. Surgery should not be reported as an outcome of an adverse event if the purpose of the surgery was elective or diagnostic and the outcome was uneventful.
2. Hospitalization or prolonged hospitalization required to allow efficacy measurement for the study.
3. Hospitalization or prolonged hospitalization for therapy of the target disease of the study, unless it is a worsening or increase in frequency of hospital admissions as judged by the clinical investigator.

11.2.1 Serious Adverse Experience Reporting

The PI will document all SAEs that occur (whether or not related to study drug) on an SAE Report Form. The collection period for all SAEs will begin after informed consent is obtained until all procedures for the final study visit have been completed.

All SAE Report Forms will be reviewed by the PI. SAE reports that are both related and unexpected will be sent to FDA within one business day of learning of the event. SAE reports that are both related and unexpected will also be forwarded to the UW Institutional Review Board, in accordance with UW Standard Operating Procedures. Because this is an observational study, no data safety and monitoring board will be created for this trial. Adverse events and recruitment will be monitored by the PI and reported to the UW IRB, as described above.

12 DISCONTINUATION AND REPLACEMENT OF SUBJECTS

12.1 Early Discontinuation of Study Drug

A subject may be discontinued from study treatment at any time if the subject, the investigator, or the Sponsor feels that it is not in the subject's best interest to continue. The following is a list of possible reasons for study treatment discontinuation:

- Subject withdrawal of consent
- Subject is not compliant with study procedures
- Adverse event that in the opinion of the investigator would be in the best interest of the subject to discontinue study treatment
- Protocol violation requiring discontinuation of study treatment

- Lost to follow-up
- Sponsor request for early termination of study
- Positive pregnancy test (females)

If a subject is withdrawn from treatment due to an adverse event, the subject will be followed and treated by the Investigator until the abnormal parameter or symptom has resolved or stabilized.

All subjects who discontinue study treatment should come in for an early discontinuation visit as soon as possible and then should be encouraged to complete all remaining scheduled visits and procedures.

All subjects are free to withdraw from participation at any time, for any reason, specified or unspecified, and without prejudice.

Reasonable attempts will be made by the investigator to provide a reason for subject withdrawals. The reason for the subject's withdrawal from the study will be specified in the subject's source documents Refer to Section 10 for early termination procedures.

12.3 Withdrawal of Subjects from the Study

A subject may be withdrawn from the study at any time if the subject, the investigator, or the Sponsor feels that it is not in the subject's best interest to continue.

All subjects are free to withdraw from participation at any time, for any reason, specified or unspecified, and without prejudice.

Reasonable attempts will be made by the investigator to provide a reason for subject withdrawals. The reason for the subject's withdrawal from the study will be specified in the subject's source documents. Subjects who withdraw after Visit 2 but prior to Visit 10 will be encouraged to come in for a final visit (and the procedures to be followed would include those for their next scheduled visit).

12.4 Replacement of Subjects

Subjects who withdraw from the study treatment will be replaced.

Subjects who withdraw from the study will be replaced.

13 PROTOCOL VIOLATIONS

A protocol violation occurs when the subject or Sponsor-Investigator fails to adhere to significant protocol requirements affecting the inclusion, exclusion, subject safety and primary endpoint criteria. Protocol violations for this study include, but are not limited to, the following:

- Failure to meet inclusion/exclusion criteria
- Use of a prohibited concomitant medication
- Failure to comply with Good Clinical Practice (GCP) guidelines will also result in a protocol violation. The Sponsor-Investigator will determine if a protocol violation will result in withdrawal of a subject.

When a protocol violation occurs, it will be discussed with the Sponsor-Investigator and a Protocol Violation Form detailing the violation will be generated. This form will be signed by a

Sponsor-Investigator. A copy of the form will be maintained in the regulatory binder and in the Sponsor-Investigator's files.

14 STATISTICAL METHODS AND CONSIDERATIONS

14.1 Data Sets Analyzed

All participants who receive the study drug (D₆-25(OH) D₃ Solution for Injection) will be included in the safety analysis.

14.2 Demographic and Baseline Characteristics

The following variables collected at re-screening will be summarized: age, gender, medical comorbidities, medications used, height, weight, body mass index, laboratory values (including calcium, phosphorus, albumin, vitamin D binding protein, parathyroid hormone, fibroblast growth factor-23), and adiposity measured by DXA.

14.3 Analysis of Primary Endpoint

We will compare the distribution of D₆-25(OH)D₃ clearance measured during this study to the distribution of D₆-25(OH)D₃ clearance measured in the same participants in the unsupplemented state during CLEAR or CLEAR-CF. We will use the paired t-test to test differences in these distributions. We will use linear regression with multiplicative interaction terms to explore whether CKD or CF modify the D₆-25(OH)D₃ clearance response to vitamin D₃ supplementation..

14.4 Analysis of Secondary Endpoints

Analyses of secondary endpoints will parallel those of the primary endpoint.

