5.2 Secondary Efficacy Endpoints

- AUC of labeled D₆-25(OH)D₃
- Terminal half-life of labeled D₆-25(OH)D₃

- Volume of distribution in the central compartment of labeled D₆-25(OH)D₃
- Metabolic formation clearance (metabolite/parent AUC ratio) for metabolites of labeled D₆-25(OH)D₃

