8.4.1 Dosage/Dosage Regimen

Each participant will receive a single intravenous dose of D₆-25(OH) D₃ Solution for Injection, 20 µg/mL. We will use estimated blood volume based on body weight to achieve a target concentration of 5 ng/mL D₆-25(OH) D₃. The target of 5 ng/mL was selected because it will allow precise tracking of circulating deuterated D₆-25(OH) D₃ concentration throughout follow-up (based on known limits of detection for our assay) without substantially perturbing underlying vitamin D status. Theoretically, the dose required to achieve a 5 ng/mL increment in deuterated 25(OH)D₃ concentration can be calculated as the targeted peak concentration multiplied by the volume of distribution, which for 25(OH)D₃ is expected to be equal to blood volume. We will use the formula of Nadler et al (1962) to estimate blood volume for each participant. We will begin the study by administering to each participant a dose of 5 ng/mL x estimated blood volume. A typical dose would be 32 µg (1.6 mL) for an 85 kg individual. We have verified in CLEAR and CLEAR-CF that we achieve target D₆-25(OH) D₃ concentrations with this approach.

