9.1.4 Physical Examination

Height and weight will be measured at the Re-screening visit and at Baseline (Study Day 0). When prompted by reports or suspicion of potential adverse effects during follow-up, physical exam findings will be documented by qualified staff (MD, NP, RN, or PA) and will be followed by a physician or other qualified staff immediately or at the next scheduled visit, as indicated.

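### Tracer AUC is compared between studies without dividing by dose, so any systematic change in the weight-based dose would appear as a change in AUC (minor; one secondary endpoint).

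*Combined protocol and SAP*

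**What the plan says.** - **Endpoint.** The synopsis and Section 5.2 list "AUC of labeled D₆-25(OH)D₃" as a secondary endpoint. Neither place mentions dose normalisation.
- **Analysis.** Section 14.4: "Analyses of secondary endpoints will parallel those of the primary endpoint". The primary analysis in Section 14.3 compares each participant with their own CLEAR or CLEAR-CF value: "We will use the paired t-test to test differences in these distributions". It adds regression with interaction terms for chronic kidney disease (CKD) and cystic fibrosis (CF).
- **Dose.** Section 8.4.1: "We will begin the study by administering to each participant a dose of 5 ng/mL x estimated blood volume". Sections 8.4 and 8.4.1 base estimated blood volume on body weight. On the earlier studies, Section 8.4.1 adds: "We have verified in CLEAR and CLEAR-CF that we achieve target" concentrations with the same approach.
- **Body size.** Section 9.1.4 has height and weight measured again for this study, at Re-screening and at Baseline.
- **Clearance.** Section 5.1 defines clearance as dose over AUC and plans it both with and without a body-size adjustment. No adjustment is stated for AUC.

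**The concern.** In the primary endpoint the dose is divided out. In raw AUC it is not. If participants on average receive a larger or smaller dose than they did in CLEAR or CLEAR-CF, AUC shifts by the same proportion even when metabolism has not changed. The paired test on AUC would then mix dose change with clearance change, and it could disagree with the primary result for that reason alone.

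The interaction analysis is open to the same problem. If mean dose change differed between participants with and without CKD or CF, raw AUC could show effect modification that clearance does not.

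The time between doses leaves room for weight to change. Section 6.1 allows an approach up to 18 months after CLEAR or CLEAR-CF is completed. Section 10.2 allows re-screening up to 180 days after screening, and Section 10.3 places dosing within 90 days after that. If screening follows the approach at once, this is about 18 + 6 + 3 = 27 months from completion.

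**Working it through.** **Inputs from the documents.** Baseline clearances 319, 322, 332 and 431 mL/day, n = 20, 90% power and 5% type 1 error (Section 14.6). Typical dose: "A typical dose would be 32 µg (1.6 mL) for an 85 kg individual" (Section 8.4.1). Expected clearance increase above 50% (Section 14.6). The synopsis prints the clearance figures in mL/min; mL/day is used here, and the percentages do not depend on the unit.

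**Inputs assumed.** Mean dose drift of 0% to 5% upward, and an SD of 3% for individual dose change. The documents give neither.

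**1. The plan's own figures.** The four values have mean 351 and SD 53.62, a CV of 53.62/351 = 15.3%. With a two-sided normal approximation, the minimal detectable difference is (1.960 + 1.282) × 53.62 × √(2(1 − r)) / √20. For r = 0, 0.25, 0.5, 0.75 and 0.9 this gives 54.97, 47.60, 38.87, 27.48 and 17.38 mL/day. Table 14.1 has 55, 48, 39, 27.5 and 17.5, so it reproduces. As a share of the mean, the table runs from 17.5/351 = 5.0% to 55/351 = 15.7%.

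**2. How dose enters AUC.** AUC = dose/clearance.
- 32 µg at 351 mL/day: 32,000/351 = 91.2 ng·day/mL.
- Dose 5% higher: 33,600/351 = 95.7, or +5%.
- Dose 10% higher: 35,200/351 = 100.3, or +10%.

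Clearance recomputed from dose and AUC is 351 in every case.

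**3. Effect on the paired test when clearance does not change.** 20,000 simulated trials per setting, each with 20 participants. Clearance is lognormal with CV 15.3% and correlation r on the log scale, and dose change is independent of clearance. Everyone receives 32 µg the first time, and the t-test is two-sided at 5%. Rejection rates for raw AUC:

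| r | no drift | +1% | +2% | +3% | +5% |
|---|---|---|---|---|---|
| 0 | 5.2% | 5.3% | 6.7% | 8.9% | 15.9% |
| 0.5 | 4.8% | 5.6% | 8.5% | 12.0% | 26.1% |
| 0.75 | 4.7% | 6.3% | 11.4% | 20.1% | 45.4% |
| 0.9 | 4.7% | 8.6% | 20.0% | 39.0% | 79.0% |

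For AUC divided by dose, every setting gives 4.6% to 5.3%.

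**4. Random dose change without drift.** The approximate SD of the paired difference, in percent, is √(15.3² × 2(1 − r) + 3²). At r = 0.5 it rises from 15.3% to 15.6%. At r = 0.9 it rises from 6.8% to 7.5%. The added noise is small.

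**5. If the expected effect occurs.** A 50% rise in clearance gives an AUC ratio of 1/1.5 = 0.667. A mean dose change of −10% gives 0.9/1.5 = 0.60, and +10% gives 1.1/1.5 = 0.73.

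**The case against.** The best defence is that raw AUC has a meaning under this dosing rule. If dose is exactly 5 ng/mL times estimated blood volume in both periods, then AUC = 5 / (clearance ÷ blood volume). This is the reciprocal of clearance per unit of blood volume, a form of size-adjusted clearance. A gap between AUC and absolute clearance is then not arbitrary. That is correct as algebra. But the plan does not define or interpret AUC this way, and Section 5.1 already provides for size-adjusted clearance, so normalising AUC loses nothing.

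A second objection is that the fix makes AUC redundant, since AUC divided by dose is simply 1/clearance. This stands. It is a reason to label the result as non-independent, or to leave raw AUC untested.

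A third is that the size of the problem is assumed. This also stands. If blood volume were proportional to weight (an assumption), a 5% mean drift at 85 kg would need 0.05 × 85 = 4.25 kg, on average and in one direction. Nothing in the documents suggests such a shift. The largest rates in the table also need r = 0.9, and Section 14.6 calls the correlation unknown.

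Two stronger readings are tempting. A reader might infer that the protocol orders a fresh dose calculation. That follows reasonably from the weight-based rule, the new weight measurement and the use of the same approach in CLEAR, but it is not stated. A reader might also lengthen the 27 months by adding CLEAR's own follow-up, but the documents do not give its length.

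**Conclusion.** The point holds as a minor defect in one secondary endpoint. Followed as written, the AUC test responds to dose change as well as clearance change. Bias needs a systematic mean drift in dose; random changes add only a little noise. Under the assumed drift of 1% to 5%, the false-positive rate is about 6% to 26% at r = 0.5 and 9% to 79% at r = 0.9. With no mean drift it stays near 5%. The conclusion rests on the inference that the dose is recalculated and on drift sizes that the documents do not supply.

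The documents do not support reading this as a threat to the trial's main result. The primary endpoint divides out the dose. Half-life, central volume and the metabolite/parent AUC ratio do not depend on dose under linear kinetics. Nor would the expected clearance increase of more than 50% be hidden or reversed: the AUC ratio stays between 0.60 and 0.73 for dose changes within ±10%. The risk is confined to a small or absent effect, and to the subgroup comparisons.

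**What to change.** In the synopsis, Section 5.2 and Section 14.4, choose one of two wordings:

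- Define the tested endpoint as AUC divided by administered dose, in both periods, and state that it is the reciprocal of clearance and not independent evidence.
- Keep raw AUC as a descriptive summary without a test, shown beside the dose given in each study.

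Either is a change of a phrase. No new data are needed, because the clearance calculation already requires the administered dose from both studies.
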